## 1 Introduction

This document is a clinical investigation plan (CIP) for the clinical investigation of the SJM™ Invisible Trial System with market-approved lead(s). This clinical investigation is intended to evaluate anatomic versus targeted lead placement for BurstDR™ therapy during the trial evaluation period.

This clinical investigation is sponsored by Abbott (ABT).

This clinical investigation will be conducted in accordance with this CIP. All parties involved in the conduct of the clinical investigation will be qualified by education, training, or experience to perform their tasks and this training will be documented appropriately.

## 2 Background and Justification for Clinical Investigation

Spinal cord stimulation (SCS) reduces pain and improves function and quality of life for patients with chronic, intractable pain. Typically, patients, who are candidates for SCS have failed other treatment options, are recommended by their physician to participate in a SCS trial evaluation period with percutaneously implanted leads powered by an external generator. The trial evaluation period can span from 3 to 30 days (or more) depending on the patient needs, physician's discretion, and regional reimbursement requirements. Successful trial evaluation of the SCS device is contingent upon adequate pain relief and/or functional improvements as assessed by the patient and the physician. Standard of care for "successful" trial evaluations is driven by reimbursement in most countries, which typically includes, but may not be limited to, patient assessment of 50% pain relief and willingness to proceed to a permanent implantable pulse generator (IPG).

Until recently, SCS trials and permanent systems delivered tonic stimulation (See Figure 1), which delivers a stream of pulses at consistent amplitude, pulse width and frequency. Tonic stimulation produces paresthesia, a tingling sensation, in the areas of stimulation coverage. Outcomes during the trial evaluation are thought to predict long-term success with therapy, though evidence in the literature is sparse due to poor reporting of trial experiences. Rates of successful trial evaluations leading to permanent implant vary in the literature (41% to 71% or more).

Recently, BurstDR™ stimulation mode was approved in Europe and the US for use in permanently implanted systems (CE mark: March 2014 and PMA: October 2016). BurstDR™ programmable parameters include (A) the burst train, (B) the time of onset of the burst train to the time of onset of the next burst train (burst rate), and (C) the rate of pulses within each train (intra-burst rate) (See Figure 2). While BurstDR™ features a group of pulses that are repeated in an on/off pattern, it is unlike cycle mode because it mimics the natural signaling of burst neurons utilizing closely spaced stimuli. The amplitudes used for BurstDR™ stimulation are reported to be significantly lower than those traditionally used for tonic stimulation which results in pain suppression that is generally sensation free (e.g., does not produce paresthesia).

The St. Jude Medical™ Invisible Trial System, capable of delivering both tonic and BurstDR™ stimulation, was approved (CE mark: June 2015 and PMA: July 2015). The Invisible Trial System consists of an External Pulse Generator (EPG) and a Patient Controller. The EPG is smaller than other systems on the market and is designed to be bandaged to the patient's back, which eliminates access to connector wires to reduce dislodgement and lead migrations. Furthermore, the EPG is controlled wirelessly via Bluetooth™ low energy technology with the Patient Controller.

Lead placement for BurstDR™ has proceeded to use temporary tonic stimulation such that the sensory qualities of tonic programming (paresthesias) can be used to elicit feedback from patients and ensure the leads are properly placed and programmed. Because BurstDR™ results in sensation-free therapy for most patients, it has been proposed that anatomic placement of the leads could result in effective therapy while

reducing procedure times during both the trial evaluation and permanent system implants. No studies have investigated this procedural variation, to date.

Additionally, there is no published literature for the use of BurstDR™ or the Invisible Trial System during the trial evaluation period, and, thus, no quantitative examination of the rate of successful qualification for permanent implant when this therapy mode and device is used during the trial evaluation period.

Therefore, the aims of the proposed clinical investigation are to evaluate the qualification rate of BurstDR™ in conjunction with the Invisible Trial System during the trial evaluation period for BurstDR™ therapy via anatomic versus targeted lead placement.

Figure 1: tonic pattern

[figure not shown]
[figure not shown]

Figure 2: BurstDR™ pattern

### 3 Device(s) Under Investigation

#### 3.1 Identification and Description of the Devices under investigation

##### 3.1.1 Identification

In this clinical investigation, the SJM™ Invisible Trial System is being used and consists of an External Pulse Generator (EPG), a Clinician Programmer and a Patient Controller. The components communicate with each other via wireless Bluetooth™ communication.

Table 1: Identification of Devices under Investigation

Device name	Model/Type	Manufacturer	Region/ Country	Investigational or Market Released
SJM™ Invisible Trial System	3599, 3032	SJM	EMEA/ANZ/CA/US	Market Released
Clinician Programmer (iPad Mini)	3872	SJM	EMEA/ANZ/CA/US	Market Released
Patient Controller (iPod Touch)	3873	SJM	EMEA/ANZ/CA/US	Market Released

### 3.1.2 Device Description and Intended Purpose

The SJM™ Invisible Trial System is indicated for use in subjects as an aid in the management of chronic, intractable pain of the trunk and/or limbs and is used during the trial system evaluation period. It consists of an External Pulse Generator (EPG), a Clinician Programmer and a Patient Controller. The components communicate with each other via wireless Bluetooth™ Low Energy (BLE) communication.

### 3.1.3 Device Handling and Storage

The devices used during this clinical investigation are commercially available and will be handled and stored according to the applicable product manuals and standard site practices.

## 3.2 Devices Accountability

The devices used during this clinical investigation are commercially available and device accountability is not required.

## 4 Clinical Investigation Design

### 4.1 Clinical Investigation Design

This is a randomized, controlled, single blind, multi-center clinical investigation comparing success rates for anatomically placed leads to conventional, targeted lead placement for BurstDR™ during the trial evaluation period with the SJM™ Invisible Trial System. Subjects will be blinded to treatment group and randomized in a 1:1 ratio as follows:

- Group 1 (AB): anatomic lead placement followed by BurstDR™ stimulation during an initial trial evaluation period
- Group 2 (TB): targeted lead placement followed by BurstDR™ stimulation during an initial trial evaluation period

If the subject qualifies for permanent system implant as defined in section 4.3.1 after the initial trial evaluation period, the subject will exit the clinical investigation and continue their treatment per the physician's standard of care. Subjects who do not qualify for permanent system implant as defined in section 4.3.1 after the initial trial evaluation period may participate in an extended trial evaluation period, per physician discretion, during which they will be programmed with tonic stimulation. Subjects continuing to an extended trial evaluation period will be followed through the completion of the extended trial period. At the end of the extended trial evaluation period, subjects will exit the clinical investigation.

The randomization diagram (Figure 3) and the study flow chart (Figure 4) are shown below.

Figure 3: Randomization Diagram

[figure not shown]
[figure not shown]

Figure 4: Study Flow Chart

## 4.2 Objectives

### 4.2.1 Primary Objective

The primary objective in this clinical investigation is to demonstrate that the qualification rate with anatomic lead placement is non-inferior to the qualification rate with targeted lead placement (tonic paresthesia guided) for the BurstDR™ stimulation trial evaluation period.

### 4.2.2 Secondary Objective

The secondary objective of this clinical investigation is to establish a higher rate of physician preference for anatomic lead placement procedure.

## 4.3 Endpoints

There is one primary endpoint and one secondary endpoint in this clinical investigation.

### 4.3.1 Primary Endpoint

The primary endpoint is the qualification rate for permanent system implant at the end of the initial trial evaluation period.

Qualification for permanent system implant is defined by a composite in which a subject meets all of the following conditions:

- >50% patient reported pain relief (PRP) at the end of the trial evaluation
- Trial evaluation period lasted for a minimum of 3 days
- Physician recommends subject for permanent system implant
- Subject reports a willingness to pursue a permanent system implant

Subjects are not qualified for permanent system implant if they meet **both** of the following:

- ≤50% PRP (patient reported pain relief) at the end of the trial evaluation
- Trial evaluation period lasted for a minimum of 5 days

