### 4.3.3 Descriptive Endpoint(s)

Descriptive endpoints are reported using only summary statistics and no hypothesis tests will be performed.

1. Overall procedure time (in-room to out-room), implant procedure time (needle-in to needle-out), and total time of intra-operative fluoroscopy exposure for each randomized group and stratified by number of leads and lead type (permanent lead or temporary lead).
2. Programming time required for each randomized group.
3. Change from pre-implant Numerical Rating Scale (NRS) in each randomized group to end of initial trial evaluation period and to the end of the extended trial evaluation period, as applicable.
4. Number of subjects in each randomized group who have affirmative assessment for each of the independent criteria required for qualification for permanent implant.

5. Proportion of subjects in each randomized group who do not qualify for permanent implant, however do proceed with permanent implant per physician discretion.
6. Time from trial system implant to >50% PRP measured by the number of days (also known as “wash-in period”).
7. Rate of serious adverse device effects (SADE) in each group.
8. Number and proportion of meaningful lead migrations\* during the initial trial evaluation periods by treatment group.
9. Number and proportion of meaningful lead migrations\* during the initial trial evaluation period in subjects who have a temporary trial lead implant compared to subjects who have a permanent trial lead implant.
10. Clinician assessment of anesthesia related difficulty (assessed primarily in the procedure room for the trial) on a 5 point likert scale for each randomized group.
11. Clinician assessment of lead placement difficulty on a 5 point likert scale for each randomized group.
12. Clinician affinity (liking) for lead placement technique at the end of the trial implant procedure.
13. Permanent system qualification rate at the end of extended trial period.

\*A meaningful lead migration is defined as a lead migration resulting in the inability to program for therapeutic response.

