#### 5.4.2 Randomization and Blinding

Randomization may occur at the end of the baseline visit or just prior to surgery for trial system implant (Initial Trial Evaluation Period Start) Visit.

Subjects will be randomized (1:1) using random permuted blocks of varying length and stratified by site. Subjects will be blinded to treatment group and treated in two groups as follows:

1. Group 1 (AB): anatomic lead placement followed by BurstDR™ stimulation during initial trial evaluation period
2. Group 2 (TB): targeted lead placement followed by BurstDR™ stimulation during initial trial evaluation period

Randomization assignment will be communicated to the site via the Randomization Application available in the EDC Site Portal.

Regardless of sedation, subjects will not be able to distinguish what implant technique (anatomic or targeted) is utilized without intimate knowledge of SCS programming, and with standardizing subject

interactions, the subjects will remain blinded to the treatment group. Implanting physicians and surgical support staff must follow the specific guidelines for the lead placement techniques and therefore cannot be blinded, but will be provided with a standardized script to assist with subject interaction as a way to minimize the risk of disclosing randomization assignments. Additionally, sites will be instructed to schedule study visits to restrict study subjects from being in the clinic at the same time, which aims to minimize subject to subject communication. Prior to study exit and before being unblinded, subjects will be asked about their memory for intra-operative testing as an assessment of the blind. Intra-operative testing is the key distinguishing feature between the techniques, so assessment of memory for experience will help to establish the status of the blind for each subject.

A Blinding Plan will be maintained separately which will include a listing of all parties involved in the study to manage workflow and identification of blinded and unblinded information.

[figure not shown]

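### The primary composite requires a physician recommendation with no stated blinding safeguard, and the plan specifies no interval for pain relief alone against the 15-point margin

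*Combined protocol and SAP*

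**What the plan says.** Section 4.3.1, repeated in section 6.1.1, sets an all-conditions rule: "Qualification for permanent system implant is defined by a composite in which a subject meets all of the following conditions". The conditions are ">50% patient reported pain relief (PRP) at the end of the trial evaluation", a trial period of at least 3 days, "Physician recommends subject for permanent system implant", and the subject's willingness to go on to a permanent system.

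On blinding, section 5.4.2 says "Subjects will be blinded to treatment group and treated in two groups as follows", but also "Implanting physicians and surgical support staff must follow the specific guidelines for the lead placement techniques and therefore cannot be blinded". It adds: "A Blinding Plan will be maintained separately which will include a listing of all parties involved in the study". The text describes no blinded or independent person who makes the recommendation.

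The 15-point margin in section 6.1.1 applies to the composite, and section 6.7 ties study success to that endpoint alone. Relief by itself appears in descriptive endpoint 4 (sections 4.3.3 and 6.5): "Number of subjects in each randomized group who have affirmative assessment for each of the independent criteria required for qualification for permanent implant". Descriptive endpoints receive summary statistics without hypothesis tests. The secondary objective (section 4.2.2) is to "establish a higher rate of physician preference for anatomic lead placement procedure".

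**The concern.** Pain relief is the component reported by the blinded party. The recommendation is a judgement, probably made by someone who knows the arm, in a trial that also tests whether physicians prefer one of the two techniques.

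Under the all-conditions rule, the composite difference between arms equals the PRP difference only if every PRP responder in both arms is also recommended and willing. Otherwise the two can differ in either direction. The direction that matters in a non-inferiority trial is a true loss of relief that looks smaller in the composite. This can happen in two ways:

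- Responders in the targeted arm (TB) are recommended less often than responders in the anatomic arm (AB).
- Recommendation or willingness is below 100% to the same degree in both arms, and unrecommended responders count as failures. Both rates are then multiplied by the same fraction, which pulls their difference towards zero.

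In either case the plan could declare success while relief is worse by the full margin. The only planned check would be a table of counts.

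**Working it through.** **Inputs.** The documents give the all-conditions rule, the 15-point margin and 1:1 allocation. Sections 6.1.1.1, 6.1.1.2 and 6.4 carry no text in the available version, so there is no planned sample size, alpha or power to reproduce. That is not counted as a fault. The following are assumptions:

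- One-sided alpha 0.025, with an unpooled normal approximation.
- 113 to 174 per arm. For scale, 80% power at one-sided 0.025 needs 144 per arm for equal rates of 71% and 175 for equal rates of 50%.
- True PRP >50% rates of 71% (TB) and 56% (AB), a loss equal to the margin. The 71% is the upper of the two literature rates for successful trials in section 2, borrowed here as a PRP rate.
- All responders reach 3 days.
- The recommendation rates r among responders are illustrative. Nothing in the documents supports particular values.

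**Step 1: unrecommended responders count as failures.** This follows the denominator in section 6.1.1, which is all subjects who complete the initial period. Composite rate q = p × r. Probability of declaring non-inferiority = Φ((q_AB − q_TB + 0.15)/SE − 1.96), with SE = √([q_AB(1 − q_AB) + q_TB(1 − q_TB)]/n).

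Worked case, 98% versus 95%, n = 174: q_AB = 0.56 × 0.98 = 0.5488 and q_TB = 0.71 × 0.95 = 0.6745, difference −12.6 points. SE = √((0.2476 + 0.2196)/174) = 0.0518. Φ(0.0243/0.0518 − 1.96) = Φ(−1.49) = 6.8%.

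**Step 2: unrecommended responders are dropped.** Section 6.1.1.3 limits the analysis to subjects who meet the qualified or the not-qualified definition. The latter requires PRP of 50% or less, so a responder who is not recommended meets neither. Then q′ = pr/(1 − p(1 − r)), and the arm size falls by the same denominator. For AB at 98%: 0.5488/0.9888 = 55.5%. For TB at 95%: 0.6745/0.9645 = 69.9%. For TB at 92%: 0.6532/0.9432 = 69.3%.

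| Recommended, AB vs TB | Difference, counted as failures | P(non-inferiority), 113–174 per arm | Difference, dropped | P(non-inferiority), 113–174 per arm |
|---|---|---|---|---|
| 100% vs 100% | −15.0 | 2.5% | −15.0 | 2.5% |
| 98% vs 95% | −12.6 | 5.7–6.8% | −14.4 | 3.1–3.2% |
| 98% vs 92% | −10.4 | 10.5–13.9% | −13.8 | 3.9–4.3% |

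**Step 3: dilution without bias.** With 90% in both arms and the failure rule, 0.504 − 0.639 = −13.5 points and the probability is 4.2–4.7%. If these responders are dropped, 0.504/0.944 − 0.639/0.929 = −15.4 points, and the probability at 144 per arm is 2.1%. At these rates, equal dilution is therefore a problem only under the failure rule.

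**Step 4: range.** With TB PRP at 41% (the lower literature rate) and AB at 26%, the failure rule gives 4.4–4.9% for 98% versus 95% and 6.6–8.1% for 98% versus 92%. A wider gap, 100% versus 90% with PRP 56% versus 71% and 144 per arm, gives −7.9 points and 23% under the failure rule, or −12.8 points and 5.8% if dropped. To cancel the 15-point loss completely with every AB responder recommended, the TB rate would have to fall to 0.56/0.71 = 79%.

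**Step 5: after the change.** An analysis of PRP >50% alone with a true 15-point loss declares non-inferiority 2.5% of the time whatever physicians recommend. For equal rates between 41% and 71% it needs 144 to 175 per arm for 80% power. Where the composite is sized at 161 to 174 per arm (PRP 60% or 71%, r of 0.8 or 0.9), the PRP analysis has 82% to 86% power.

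**The case against.** Several stronger readings are tempting, and the documents do not support them.

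- A reader might infer that a physician who likes anatomic placement can pass AB subjects whose pain did not improve. The all-conditions rule prevents this.
- A reader might infer that the planned tables hide a loss of relief. They do not: descriptive endpoint 4 gives each criterion by arm, and endpoint 3 adds the change in pain score. A reader with the denominators could work out the difference and its interval. What is missing is a commitment to report that interval against the margin.
- A reader might take the recommender to be the unblinded implanter. This is a fair inference, but section 4.3.1 says only physician, and the Blinding Plan is a separate document that is not available here.
- A reader might treat the secondary objective as evidence of bias. The recommendation concerns a permanent system, not a placement technique, and both arms receive BurstDR through the same trial system. Preferring a technique gives no evident reason to refuse a TB responder.
- A reader might call the percentages an inflated type I error of the primary test. They are not. In the biased scenarios the composite difference really is smaller than 15 points. The error lies in reading composite success as showing that relief is preserved.

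It is also fair to say that section 6.2 justifies the composite as matching standard-of-care qualification, that the assumed recommendation rates are hypothetical, and that the effect is small if unrecommended responders are dropped. These points stand. They support keeping the composite as primary and limiting the request to one supportive analysis. They do not remove the gap, because the text does not settle which handling applies and gives relief no comparison with the margin. Detail may exist in the blank section 6.1.1.1, but this cannot be checked.

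**Conclusion.** The concern holds in a limited form. The primary endpoint includes a physician judgement with no stated blinding safeguard, and the plan specifies no between-arm estimate or interval for PRP >50% against 15 points. Under the assumed rates, a true 15-point loss of relief passes the composite test 5.7–6.8% or 10.5–13.9% of the time if unrecommended responders count as failures, and 3.1–3.2% or 3.9–4.3% if they are dropped, against 2.5% for PRP alone. The size depends on recommendation rates that the documents do not give and on a handling rule that sections 6.1.1 and 6.1.1.3 leave open. The documents do not show that differential recommendation will occur. The remedy is cheap enough that the sponsor should adopt it anyway.

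**What to change.** Keep the composite as the primary endpoint and add the following before unblinded data are seen:

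1. A supportive non-inferiority analysis of PRP >50% alone at the end of the initial trial period. Use the same method, the same 15-point margin and the same analysis set as the primary, with responders who were not recommended or not willing kept in the denominator. Holding the population constant matters: if component and population changed together, a discordant result could not be attributed to either.
2. The same analysis under the sensitivity rule of section 6.1.1.5, in which implanted subjects who do not complete the initial period count as failures.
3. The PRP confidence interval reported beside the composite, with recommendation and willingness rates among PRP responders by arm.
4. A sentence stating that a composite success not supported by the PRP interval will be described as not demonstrated on pain relief alone.
5. A statement of how a responder who is not recommended or not willing counts in the composite itself.

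The cost is one further analysis of data already collected, with no new visits. The sponsor accepts that it may be less favourable than the composite. It is also not a fully blinded measure. PRP is only as blind as the subject: section 5.6 allows interview administration of questionnaires, and section 5.4.2 checks the blind through memory of intra-operative testing.

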### 4.3.2 Secondary Endpoint

The secondary endpoint is the rate of physician preference for anatomic placement versus targeted placement at the end of the study.

